10.0 Quality Control and Quality Assurance

[name] will be responsible for quality control and quality assurance of the data collected. [name] has more than ten years of experiences in pressure ulcer research using non-invasive blood flow measurements, and she will perform the protocols in person and shadow her research team on the first two subjects. [name] will then supervise the data collection on site for the next three subjects recruited in this study. [name] will check all the data within two days of collection (paper and electronic formats). If the study team encounter any issues related to data collection, [name] is available through phone calls to address the concerns. [name] will meet with her team every two weeks to check the laboratory notes and monitor the study regularly.

11.0 Data and Safety Monitoring

The PI of this study ([name]) will be responsible for monitoring the data and safety of this study. [name] will meet with the research team every two weeks to monitor the overall conduct of the study (including issues with safety, ethics, recruitment, retention, adequacy of study design to achieve the specific aims) and provide feedback to the study team for the possible protocol amendments, and input from this study on future studies. Serious adverse events are not expected, but all such events will be reported according to the UIC IRB, and will be handled with the standard of Good Clinical Practice Guidelines including informing the PI, and IRB within 24 hours of the event, following up and reporting on the event until resolved, and subsequently reported to the PI.

The risk of breach of confidentiality is minimal since the only key to link subject ID and confidential information is a hard copy of Form A, which is locked in the file cabinet of the PI's locked office. All other data is only coded with a subject ID in hard copy and electronic file. All hard copy files with subject ID only will be stored in a locked cabinet in the PI's locked laboratory, which is three floors away from the PI's office. All electronic data are also coded and encrypted using Symantec software, and they will be stored on the laptop used to collect data, and the hard drive located in the PI's laboratory. Both computers are password protected, and the data are only accessible to the PI's team. All study personnel are trained in the maintenance of security and confidentiality of research data.

12.0 Statistical Considerations

For aims 1 and 2, paired *t*-tests will be computed to compare the interface pressure and skin blood flow during 40 minutes of AP overlay (AP protocol) vs. OR overlay (Ctrl protocol). Paired *t*-tests will also be used to compare the reactive hyperemic response during RH1 (AP protocol) vs. RH (Ctrl protocol). For aim 3, paired *t*-tests will be computed to compare the skin blood flow during OR overlay (AP protocol) vs. OR overlay (Ctrl protocol), and the reactive hyperemic response during RH2 (AP protocol) vs. RH (Ctrl protocol). SPSS will be used for all statistical analyses. Since this is a pilot study, we will test the study on 15 subjects. Results from this study will be used to calculate sample size for future studies. In case of dropout or subject decease during this study, we propose to recruit up to 20 subjects for this study.

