6.0 Study Design and Procedures

Study Design. This study uses a repeated measures design, and each subject will act as his/her own control. Each subject will undergo the two protocols in the experimental procedures: AP protocol and Control protocol. To ensure the order of the two protocols are randomized, the order of AP and Control protocols will be determined by drawing one envelope from the envelope pool. We will start with a pool of total 20 envelopes (10 envelopes indicating AP protocol first, and 10 envelopes indicating control protocol first). Once the envelope is drawn from the pool, it will not return to the pool.

Study Procedures (Research purpose). After enrollment, subjects will proceed to the following procedures: 1) experimental procedures, 2) vascular control measures, 3) pressure mapping of wheelchair and 4) blood withdraw.

1) **Experimental procedure (approximately 4.5 hours)**

Each subject will undergo two study protocols: AP and control (figure 1), and the order of the protocols will be randomized as described previously. A 30-minute washout period will be provided in between the two protocols. Two Laser Doppler flowmetry (LDF) flat probes (moor instrument, Wilmington, DE) will be taped to the sacrum and one heel to collect the skin blood flow response throughout both AP and control protocols. A whole body pressure mapping system (Xsensor, Xsensor Technology Corp., Alberta, Canada) will be used between the subject and the overlay to collect the inter pressure data. For the AP cycle, we will use four 10-minute cycles (5 minutes of high pressure and 5 minutes of low pressure).

AP protocol: The subject will first lie on his/her side quietly for 10 minutes to collect the baseline skin blood flow, followed by lying supine on the Dabir AP overlay for 40 minutes, and then side lying for 30 minutes to collect the first reactive hyperemic response. To test the effect of preconditioning, the subject will then lie supine on the OR overlay for 40 minutes followed by side lying for 30 minutes for the second reactive hyperemic response.

Control protocol: The subject will first lie on his/her side quietly for 10 minutes to collect the baseline skin blood flow, followed by lying supine on the OR overlay (AliMed®) for 40 minutes, and then side lying for 30 minutes to collect the reactive hyperemic response for control protocol.

AP	Baseline (10 min)	AP overlay (40 min)	RH 1 (30 min)	OR overlay (40 min)	RH 2 (30 min)

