9.0 Data Analysis

The MatLab program (The MathWorks Natick, MA) will be used to process the skin blood flow signal. The signals will be analyzed with two signal processing methods to characterize the responses in both time and frequency domains. Details of both methods were published previously by the PI.¹⁴

1) *Exponential curve-fitting technique:*

To select the time-domain parameters of the reactive hyperemia and heat hyperemia objectively. A tenth ordered Chebyshev I low pass filter (with cut off frequency at 0.15 Hz) will be applied to remove the noise caused by respiration and cardiac movement.¹⁰ We will use a least squares model to fit the filtered reactive and heat hyperemic curves, and all parameters (including peak, time to peak, area under curve of reactive hyperemia; and first peak, second peak and time to first and second peaks, area under curve of heat hyperemia) will be derived from the fit curves.

2) *Time-frequency analysis:*

To further examine the different control mechanisms of SBF by decomposing the signal in frequency domain. Short-time Fourier transform will be used to decompose the signal by breaking the signal into short-time segments (windows), then computed Fourier analysis within each segment to calculate

spectral densities. A 256-sample Hanning window (512 seconds) will be used to compute the spectrogram.

Please see section 12.0 for details of all statistical analyses.

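### The flow and hyperaemia t-tests in section 12 use neither the baseline flow recorded before each protocol nor the randomised order; adding both is a cheap gain in precision, not the repair of an error

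*Combined protocol and SAP*

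**What the plan says.** Section 12.0 (Statistical Considerations) names paired t-tests for flow under the AP overlay against the OR overlay. It says paired t-tests "will also be used to compare the reactive hyperemic response during RH1 (AP protocol) vs. RH (Ctrl protocol"), and plans the same for aim 3: the OR load after AP against the control OR load, and RH2 against RH. It mentions no baseline, change score, covariate, order, period or carry-over term.

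Section 6.0 collects what such terms would need. In both protocols, "The subject will first lie on his/her side quietly for 10 minutes to collect the baseline skin blood flow". Also, "the order of AP and Control protocols will be determined by drawing one envelope from the envelope pool", and Form F records which order was used. Between protocols, "A 30-minute washout period will be provided in between the two protocols". The flow probes are "taped to the sacrum and one heel to collect the skin blood flow response throughout both AP and control protocols".

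Section 9.0 takes "all parameters (including peak, time to peak, area under curve of reactive hyperemia" from the fitted curves, states no baseline reference for them, and sends the reader to section 12 for all statistical analyses. The project summary (section 1.0) lists flow before loading among the paired comparisons, but section 12 does not carry this forward. A separate test of baseline would not adjust the overlay comparisons in any case.

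**The concern.** Pairing removes stable differences between subjects. It does not remove a change in resting flow within a subject between the two protocols, because baseline is measured afresh each time. Any such change stays in the paired difference as noise. A period effect common to all subjects adds to the SD of the paired differences, and also shifts their mean when the two orders are unequal in number.

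At stake is precision in a study of 15 subjects, and the SD that section 12 intends to use for sizing later studies. The point covers flow under load and hyperaemia peak and area. It does not cover interface pressure or time to peak, for which baseline flow is not an obvious covariate.

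**Working it through.** The plan states no power, alpha, effect size or SD, so there is no figure of its own to reproduce. Everything below that is not a duration or a count is an assumption.

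**Inputs from section 6.** AP protocol 10 + 40 + 30 + 40 + 30 = 150 min; Control protocol 10 + 40 + 30 = 80 min; washout 30 min; 20 envelopes, 10 per order, drawn without replacement. From section 12: 15 subjects, up to 20 recruited.

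**Assumptions.** Two-sided 0.05; SD of the paired difference = 1 apart from any period effect; effect 0.6 SD; r = correlation of the baseline difference with the outcome difference.

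**Models.** Unadjusted: paired t-test, 14 df. Adjusted: AP-minus-Control outcome difference = intercept + b1 × AP-minus-Control baseline difference + b2 × order (+1/-1), 12 df. The intercept is the treatment effect.

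**Power, n = 15, order drawn from the envelope pool** (60,000 simulated trials per case; the exact noncentral-t value for the paired test without a period effect is 0.580):

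| r | 0 | 0.3 | 0.5 | 0.7 |
|---|---|---|---|---|
| Paired t-test, no period effect | 58% | 58% | 58% | 58% |
| Adjusted, no period effect | 53% | 57% | 65% | 81% |
| Paired t-test, period effect ±0.5 SD | 49% | 49% | 49% | 49% |
| Adjusted, period effect ±0.5 SD | 53% | 57% | 65% | 81% |
| SE ratio, adjusted to paired, no period effect | 1.05 | 1.00 | 0.91 | 0.75 |

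The 49% follows directly: a ±0.5 SD period effect inflates the SD to √(1 + 0.25) = 1.118, so the standardised effect is 0.6/1.118 = 0.54. With all 20 analysed and no period effect, power is 72% against 69, 73, 81 and 93%. Pairs needed for 80% power in a later study: 24 unadjusted, against 26, 24, 20 and 15.

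**Order split.** If 15 envelopes are drawn, the chance of 8:7 either way is 2 × C(10,7) × C(10,8)/C(20,15) = 10,800/15,504 = 0.70; 9:6 has 0.27 and 10:5 has 0.03. The unadjusted mean carries 1/15, 3/15 or 5/15 of the ± period effect. An order term removes this.

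**What the timing prevents.** The second baseline starts 150 + 30 = 180 min after the first in AP-first subjects and 80 + 30 = 110 min after it in Control-first subjects. For a steady drift of g per minute, second-minus-first baseline is 180g in one order and 110g in the other. The two orders then differ by 70g with no carry-over at all.

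The same asymmetry reaches the treatment effect. For the AP load and RH1, the AP-minus-Control time gap is -180 or +110 min, a mean of -35 min with balanced orders. Assume a drift of 0.5 SD per 110 min in baseline and outcome alike:

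- Unadjusted bias: 35 × 0.5/110 = 0.16 SD in size.
- Adjusted bias: 0.16 × (1 - r) = 0.11, 0.08 and 0.05 SD at r = 0.3, 0.5 and 0.7.

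Aim 3 goes the other way. The OR load in the AP protocol starts at its minute 80 and RH2 at its minute 120, so the outcome gap is -110 or +180 min, a mean of +35, while the baseline gap still averages -35. Adjusted bias is then 0.16 × (1 + r) = 0.21, 0.24 and 0.27 SD, against 0.16 unadjusted. A simulation gave the same values for both aims.

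**Carry-over, two assumed scenarios of 0.5 SD.** If it occurs in both orders, bias is about zero in both analyses and the paired test's type I error is about 3.5%. If it occurs in AP-first subjects only, unadjusted bias is 0.25 SD when the outcome is affected. At r = 0.3, 0.5 and 0.7, adjusted bias is:

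- about 0.17, 0.13 and 0.07 SD if baseline and outcome shift equally;
- 0.25 SD throughout if only the outcome shifts;
- about 0.08, 0.12 and 0.18 SD if only the baseline shifts, where the unadjusted test has none.

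**The case against.** The strongest case for leaving section 12 alone is that an unadjusted paired t-test on a randomised within-subject comparison is a reasonable choice for a 15-subject pilot. The documents give no r; with no period effect, adjustment gains nothing below about 0.3 and loses five points of power at zero. That stands, and it makes this an improvement rather than a correction. Section 9 also refers signal processing to a publication, which may already define peak and area relative to baseline. That stands too, but does little harm: with the baseline difference as covariate, subtracting baseline leaves the intercept and its SE unchanged.

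A reader might infer more than the documents support:

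- *That the t-tests are invalid or biased by carry-over.* In both orders the last load before the second baseline is the same: 40 minutes on the OR overlay, then 30 minutes of side lying and the washout. After AP this is "side lying for 30 minutes for the second reactive hyperemic response", after Control "side lying for 30 minutes to collect the reactive hyperemic response for control protocol". Carry-over from that load would be broadly common to both orders and behave like a period effect. Bias needs carry-over specific to one order. That is possible, since AP-first subjects have had AP exposure before their control load, but nothing in the documents shows it.
- *That comparing second-minus-first baselines between orders tests for carry-over, because drift common to all subjects cancels.* It does not cancel at 180 against 110 minutes. At a 7:8 split, the contrast would also have only about 15% power for a 0.5 SD shift.
- *That the baselines are the only data on recovery.* Flow is recorded throughout both protocols, so the end of each 30-minute hyperaemia recording bears on it as well.

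**Conclusion.** The concern holds as a low-cost gain in precision. Section 12 leaves out two quantities that the study already records. Under the assumed 0.6 SD effect at n = 15, using them changes power from 58% to between 53% and 81% as r runs from 0 to 0.7. With a ±0.5 SD period effect the comparison is about 49% against the same range, so the order term then pays for itself even at r = 0. All of this rests on values of r, period effect and effect size that the documents do not give.

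Adjustment does not cure the unequal timing. Under steady drift it shrinks the bias for the AP load and RH1 but enlarges it for aim 3. It also adds bias if carry-over shifts only the baseline. The adjusted result should therefore never appear without the planned one.

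**What to change.** Add to section 12, in these or similar words:

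> For mean flow under load and for hyperaemia peak and area, at sacrum and heel separately, the AP-minus-Control difference will be regressed on the AP-minus-Control difference in 10-minute baseline flow (not mean-centred) and on protocol order (+1/-1). The intercept is the treatment effect. The planned paired t-test on the same values will always be reported beside it.

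The covariate must stay uncentred. Centred, the intercept returns to the order-adjusted difference with no baseline adjustment and too small an SE (type I error about 14% at r = 0.7).

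Also state that:

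- baseline flow is tabulated by protocol and order as description only, with the 180- and 110-minute intervals given, so that a difference between orders is not read as carry-over alone;
- the order term does not fully remove steady drift, and for aim 3 the baseline adjustment can enlarge its effect;
- the SD of the paired difference is reported with and without adjustment for future sizing.

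The cost is SAP wording; baseline and order are already recorded. The model spends two of 14 degrees of freedom, and the SE is about 5% larger if r is near zero and there is no period effect.

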2.0 Background/Scientific Rationale

Tissue ischemia is one of the main etiologies of pressure injury.¹ It is inevitable during bed-ridden and wheelchair bound conditions, such as spinal cord injury (SCI), or prolonged surgery procedure in the operating room. Active alternating pressure (AP) mattresses are covered by Medicare policy for patients with multiple/large stage 2/ stage 3 pressure injuries to relief interface pressure and prevent recurrence of pressure injuries.² Previous studies demonstrated that the protective mechanisms of AP on pressure injury include redistribution of surface pressure, and allowing more blood supplies while lying on the support surface.³⁻⁵ The Dabir AP overlay (DabirAIR™, Dabir Surfaces Inc., Hardwood Heights, IL) is low profile yet possesses similar characteristics as other AP mattresses on the market; it is intended for clinical use, such as operation room (OR) where AP mattresses may not be an option. We expect Dabir AP overlay will be beneficial to people at risk of pressure injury by maintaining the blood supply during weight bearing condition.

In addition to pressure redistribution and increasing blood supplies, we also postulate that the if an AP overlay will be beneficial to the weight-bearing skin by means of preconditioning the skin with short-term ischemia, i.e. when air cells inflate. Ischemic preconditioning is a method used to prevent tissue damage caused by ischemic events, such as stroke and myocardial infarction,⁶ by means of slowing down ATP depletion in the short-term subsequent ischemic episodes and washing out the harmful catabolites during each short-term period of reperfusion. Recently, this method is implemented to heal diabetic foot ulcer by remotely precondition the lower limb.⁷ We hypothesize that the alternating pressure characteristics of the Dabir AP overlay could be utilized as a method for preconditioning to protect weight-bearing tissue in people with SCI.

To quantify the severity of tissue ischemia, we will collect the non-invasive reactive hyperemic response as an outcome. Reactive hyperemia is characterized by sudden increase in blood flow after temporary obstruction of the blood flow. Previous studies used this response to simulate the tissue response toward ischemia in people that are at risk of pressure ulcer, such as spinal cord injury.^{8,9}

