3.0 Objectives/Aims

The objective of this study is to evaluate the protective mechanisms of Dabir AP overlay on weight bearing tissue of people with chronic spinal cord injury (SCI). Our central hypothesis is that the Dabir AP overlay will cause lower amount of interface pressure and allow more skin blood flow during weight bearing as compared to regular OR overlay. In addition, people with SCI will have better tolerance to prolonged weight bearing after preconditioned with the Dabir AP overlay.

There are three aims (with related hypotheses) for this study:

Aim 1: To determine the effectiveness of pressure redistribution with Dabir AP overlay.

Hypothesis 1. Our participants will demonstrate lower interface pressure at sacrum and heel when lying supine for 40 minutes on Dabir AP overlay as compared to that on regular OR overlay (AliMed®).

Aim 2: To examine the severity of tissue ischemia with the use of Dabir AP overlay.

Hypothesis 2a. Our participants will demonstrate greater skin blood flow at sacrum and heel when lying supine for 40 minutes on Dabir AP overlay as compared to that on regular OR overlay.

Hypothesis 1b. Our participants will demonstrate smaller reactive hyperemic response at sacrum and heel after being relieved from 40 minutes of lying supine on Dabir AP overlay as compared to that on regular OR overlay.

Aim 3: To assess the feasibility of utilizing Dabir AP overlay for ischemic preconditioning for prolonged weight bearing condition.

Hypothesis 3. With 40 minutes of preconditioning using the Dabir AP overlay, our participants will demonstrate smaller reactive hyperemic response at sacrum and heel after being relieved from the regular OR overlay as compared to that without preconditioning.

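### Randomising only protocol order leaves load position unbalanced, so the unadjusted paired t-tests are exposed to some within-session trends and Aim 3 cannot credit alternating pressure

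*Combined protocol and SAP*

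**What the plan says.** Section 6.0 sets out what is randomised: "To ensure the order of the two protocols are randomized, the order of AP and Control protocols will be determined by drawing one envelope". The pool holds 20 envelopes, 10 for each order, drawn without replacement. The AP protocol is a baseline, the AP load and a first recovery recording (RH1), after which "the subject will then lie supine on the OR overlay for 40 minutes followed by side lying for 30 minutes" (the second recording is RH2). The control protocol is a baseline, one OR load and one recovery recording (RH). Between protocols, "A 30-minute washout period will be provided in between the two protocols".

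For Aims 1 and 2, section 12.0 compares interface pressure and skin blood flow on the AP overlay with those on the control OR overlay by paired t-test. For hyperemia, paired t-tests "will also be used to compare the reactive hyperemic response during RH1 (AP protocol) vs. RH (Ctrl protocol". For Aim 3 they compare OR-load blood flow between protocols and "the reactive hyperemic response during RH2 (AP protocol) vs. RH (Ctrl protocol". No order, period or position term and no presentation by order is mentioned. The section adds: "Results from this study will be used to calculate sample size for future studies".

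Hypothesis 3 (section 3.0) expects a smaller response "after being relieved from the regular OR overlay as compared to that without preconditioning". Section 2.0 names the mechanism: "the alternating pressure characteristics of the Dabir AP overlay could be utilized as a method for preconditioning".

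**The concern.** Randomising protocol order balances protocols, not loads, because one protocol contains two loads in fixed sequence and the other contains one. A paired t-test removes differences between subjects but not differences between positions in the session. If skin blood flow or hyperemia changes with time or with repeated loading, part of that change is counted as an overlay or preconditioning effect, or hides one.

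Aim 3 has a second problem. The OR load after AP is never a first load, and the design has no OR load preceded only by another OR load. A smaller RH2 could therefore come from alternating pressure, from any earlier 40-minute load, or from time in the session.

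The results are also meant to size later studies. A gap between the two orders would widen the SD of the paired differences and carry into those calculations.

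**Working it through.** **Inputs (section 6.0).** AP protocol 10 + 40 + 30 + 40 + 30 = 150 min; control 10 + 40 + 30 = 80 min; washout 30 min. Total 260 min = 4.33 h, consistent with the stated duration of about 4.5 hours. There is no power calculation to reproduce: section 12.0 gives 15 subjects (up to 20 recruited) as a pilot number, without alpha, effect size or SD.

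**Load position and onset**

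| Order | AP | OR after AP | Control OR |
|---|---|---|---|
| AP first | 1 (10 min) | 2 (80 min) | 3 (190 min) |
| Control first | 2 (120 min) | 3 (190 min) | 1 (10 min) |
| Mean at 1:1 | 1.5 (65 min) | 2.5 (135 min) | 2.0 (100 min) |

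If a share p of subjects is AP-first, the mean position offset is 1 - 3p for AP minus control and 2 - 3p for OR after AP minus control. The two always differ by one position, so no split makes both zero.

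**Bias from position effects f1, f2, f3 at 1:1**
- AP minus control: [(f1 - f3) + (f2 - f1)]/2 = (f2 - f3)/2.
- OR after AP minus control: [(f2 - f3) + (f3 - f1)]/2 = (f2 - f1)/2.

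**Linear drift, per unit per hour**
- 1:1: (-180 + 110)/2 = -35 min = -0.58 h for AP minus control; (-110 + 180)/2 = +35 min = +0.58 h for Aim 3.
- 8 AP-first, 7 control-first: -670/15 min = -0.74 h and +380/15 min = +0.42 h. At 7:8 these become -0.42 and +0.74.
- If 15 of the 20 envelopes are drawn, one of these two splits has probability 2 x C(10,8) x C(10,7)/C(20,15) = 10,800/15,504 = 69.7%.

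**Step of size d after the first load**
- 1:1: 0 for AP minus control; +0.50d for Aim 3.
- 8:7: (-8 + 7)/15 = -0.07d and 7/15 = +0.47d.

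**Illustrative consequences for Aim 3.** Assumptions: units of within-subject SD, independent errors, two-sided 5% level, 100,000 simulated trials per scenario.
- Chance of a significantly smaller RH2 when alternating pressure itself adds nothing (nominal 2.5%): at 8:7, 8.2% with a step of -0.5 SD and 18.6% with -1 SD; at 10:10, 10.8% and 28.2%.
- Opposite sign: at 8:7, power for a true 1 SD preconditioning effect falls from 72% to 24% with a +1 SD step.

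**Variance of paired differences at 8:7.** Ratio = 1 + [8 x 7/(15 x 14)] x g²/2, where g is the gap between orders in the paired difference. Under drift, g = (180 + 110)/60 = 4.83 h x drift, giving 1.19 at 0.25 SD/h and 1.78 at 0.5 SD/h. Under a 1 SD step, g = 2 for AP minus control (ratio 1.53) and g = 1 for Aim 3 (ratio 1.13).

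**The Aim 3 comparator.** In AP-first subjects, the load treated as not preconditioned follows both an AP load and an OR load. Unloaded time before it is 30 (RH2) + 30 (washout) + 10 (baseline) = 70 min, against 30 min between the AP and OR loads inside the AP protocol.

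**The case against.** The strongest reply is that Hypothesis 3 is worded against no preconditioning, that Aim 3 is about feasibility, and that section 2.0 also describes preconditioning as short-term ischemia, which is not obviously unique to alternating pressure. If any earlier load counts, a smaller later response is partly the hypothesised effect. This stands: the 8.2% to 28.2% figures are false-positive rates only on the AP-specific reading. It does not help a conclusion that credits alternating pressure.

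The trend sizes are assumed, and some are large: 0.5 SD/h means 1.5 SD between the onsets of loads 1 and 3. Under linear drift at 8:7 the two-sided type I error hardly moves (5.3% and 2.2% at 0.5 SD/h). For interface pressure, the documents give no reason to expect a trend. These points stand too.

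The washout, with 70 unloaded minutes in all, is the protocol's provision against carry-over. It may suffice, but the documents do not show that it does, and it does not remove a time trend.

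Each protocol has its own baseline, but section 12.0 does not plan to subtract it. Doing so would cancel linear drift in Aims 1 and 2 but leave (80 - 10)/60 = 1.17 per unit of hourly drift in Aim 3.

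A reader might infer that any trend biases every test. The formulas above show otherwise: at 1:1, AP minus control is untouched if positions 2 and 3 do not differ, and Aim 3 is untouched if positions 1 and 2 do not differ.

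**Conclusion.** The point holds as exposure. Load position is unbalanced by design, section 12.0 does nothing about it, and certain trends would pass into the planned contrasts. A steady drift moves the two contrasts in opposite directions: falling hyperemia would favour apparent preconditioning in Aim 3 and count against AP in the RH1 comparison, and rising hyperemia would do the reverse. A step after the first load affects mainly Aim 3.

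A reader might go further and infer that the results will be biased or that Aim 3 is worthless. The documents support neither. They give no size or sign for any trend, and with no trend there is no position bias. Aim 3 can still address earlier loading against none, provided position is considered and the washout is adequate. It cannot attribute a difference to alternating pressure, and no analysis of these data can supply the missing OR-then-OR comparator.

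The numerical illustrations rest on assumed trends, independent errors and an assumed 5% level. For a pilot this is a cheap improvement worth making, not a fatal flaw.

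**What to change.** Keep the paired t-tests and add to section 12.0:

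1. For each contrast, report results by protocol order and a position-adjusted sensitivity estimate. For each subject, take the load-1 value and the load-3 value, each minus the mean of that subject's three loads. AP minus control is the AP-first mean minus the control-first mean of the load-1 score. OR after AP minus control is the control-first mean minus the AP-first mean of the load-3 score. Compare orders by Welch's t-test and show both estimates with 95% CIs. Do not require both to be significant: with no trend, that rule would cut power for a 1 SD effect at 8:7 from 72% to 55%.
2. State that the adjusted contrast assumes additive position effects and no carry-over, which two sequences cannot test; that it removes any generic prior-load effect; and that in Aim 3 it is more exposed than the paired test to an AP effect persisting into control OR (it loses 2/3 of that effect, against 8/15 = 0.53 at 8:7).
3. State whether preconditioning means AP-specific or any prior load. Limit the Aim 3 conclusion so that a difference between RH2 and control RH is not attributed to alternating pressure rather than to any prior load or time in session.
4. For future sample sizes, report the SD of paired differences pooled within order beside the raw SD.

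A by-order comparison of the two baselines may be shown descriptively, but it cannot separate drift from residual carry-over.

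**Cost.** SAP wording and one two-sample comparison per contrast; order is already recorded on Form F. At 8:7, with no trend, the adjusted standard error is sqrt(2/3 x (1/8 + 1/7)) = 0.423, against sqrt(2/15) = 0.365 for the paired test, about 16% larger. The 95% CI is 1.157 x 2.160/2.145 = 1.17 times as wide. Because load 2 starts at 80 min in one order and 120 min in the other, about (40/60)/3 = 0.22 per unit of hourly drift remains. A subject missing any load drops out of the adjusted estimate.
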